### **3.2 Outcomes Measurements**

Outcomes Measurements will be assessed at 12 months. Additional assessments may be made for interim (3, 6, 9-month) time points. Where applicable, changes from baseline will be evaluated. Baseline data will be defined as data provided at the initial Fitting Visit. If the patient was previously using the Eclipse System (e.g. joins the registry at a yearly follow-up/renewal), her baseline values will be omitted, and she will be excluded from analyses that require a baseline value.

The PGI-I, assessed as part of the Eclipse Experience Assessment, assesses changes from baseline in the control of bowel leakage, but does not have a baseline measurement. Instead, it is rated on a 7-point scale, where 1 is "Very much better" and 7 is "Very much worse". For a given time point, the average PGI-I score will be computed as the mean score across all completed assessments. Other Eclipse Experience Assessment questions will be summarized descriptively.

Fitting Metrics will be collected at the fitting visits, and summarized using descriptive statistics.

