### **2.5.3 Eclipse Experience Assessment**

Subjects will be asked, at in-office visits (fitting follow-ups and 12-month visits), to provide feedback on several Eclipse Experience questions related to perceptions of device comfort, satisfaction with usage and features, and impact on daily activities. This assessment includes the Patient Global Impression of Improvement (PGI-I), a validated global index that may be used to rate the response of a condition to a therapy on a scale from 1 (Very much better) to 7 (Very much worse). The PGI-I will be used to assess improvement of accidental bowel leakage in comparison to how it was prior to joining the registry or starting with Eclipse.

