### **3.1 Analysis Population**

The Analysis Data Set (ADS) will include all subjects who consent to participate in the PURSUIT registry and have at least an initial fitting, or, in the case of a patient already using Eclipse, be administered an annual renewal Eclipse.

---

 Vaizey, CJ, et al Gut 1999;44:77-80 doi:10.1136/gut.44.1.77

 Maeda Y. Does the St. Mark's incontinence score reflect patients' perceptions? A review of 390 patients. *Dis Colon Rectum*. 2008 Apr;51(4):436-42

For any analyses that require a comparison to baseline data, or data collected at the initial fitting visit, patients who enroll at their Eclipse renewal will be omitted from the ADS, as they will not have baseline or fitting metrics.

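### The 12-month PGI-I mean appears to pool newly fitted women with renewal enrollees who have used the device about twice as long, and no single reference point for the rating is fixed

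*Protocol*

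**What the plan says.** The registry enrolls both new users and women already using Eclipse who come for an annual renewal (Protocol Synopsis, 2.2, 2.3). Section 3.1 admits the second group to the analysis set provided they, "in the case of a patient already using Eclipse, be administered an annual renewal Eclipse". It then limits their role: for analyses needing baseline or initial-fitting data, "patients who enroll at their Eclipse renewal will be omitted from the ADS, as they will not have baseline or fitting metrics". Section 3.2 repeats the restriction, saying of such a patient that "she will be excluded from analyses that require a baseline value".

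On timing, 3.2 says "Outcomes Measurements will be assessed at 12 months", and on baseline, "Baseline data will be defined as data provided at the initial Fitting Visit".

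On the PGI-I, 3.2 says that it "assesses changes from baseline in the control of bowel leakage, but does not have a baseline measurement", and then gives the summary: "For a given time point, the average PGI-I score will be computed as the mean score across all completed assessments". No split by type of enrollee is mentioned. Section 2.5.3 describes the rating as made "in comparison to how it was prior to joining the registry or starting with Eclipse".

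**The concern.** The PGI-I is named within the third outcome measure in the synopsis, and 12 months is the planned assessment time. Three things are unsettled or mixed in the way its mean is defined.

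- **Who is in it.** The exclusion of renewal women turns on the need for a baseline value. Section 3.2 describes the PGI-I both as a change from baseline and as having no baseline measurement, so the rule can be read either way.
- **What duration it describes.** If renewal women are in, the 12-month label covers two different lengths of use. Renewal women have, by definition, continued as far as a renewal, whereas a new user enters the analysis set with an initial fitting alone.
- **What the rating is compared with.** Section 2.5.3 joins two reference points with *or* and does not assign them to a type of enrollee. They nearly coincide for a new user. For a renewal user they lie about a year or more apart, and before joining she was already on the device.

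The mean would then depend on a new/renewal mix that the protocol does not control, and it would be hard to read as improvement after starting Eclipse. A later analysis plan can split the groups, but it cannot recover a common reference point once women have answered against different ones.

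**Working it through.** The protocol gives no PGI-I target, effect size or sample-size derivation (150 is only an enrollment cap), so there is no figure to reproduce. The check is a reading of the text followed by simple mixture arithmetic.

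**Step 1: are renewal women in the mean?** Three statements bear on this.

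- 3.1 includes them in the analysis set and omits them only where a comparison with baseline or initial-fitting data is needed. The reason given is that they lack those data.
- 3.2 excludes them only where a baseline value is required.
- 3.2 says the PGI-I has no baseline measurement and averages it over all completed assessments.

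A renewal woman can complete the PGI-I, so the reason for excluding her does not apply. Inclusion is the more natural reading. The contrary reading comes from the clause that calls the PGI-I a change from baseline.

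**Step 2: duration of use at the 12-month rating.**

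- A woman commits to a year of use of an Insert (1.5.3) and renewal is annual, so a renewal enrollee has at least about 12 months of prior use.
- The annual visit comes about one year after enrollment (2.3).
- New user: about 12 months. Renewal user: at least about 12 + 12 = 24 months.

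The 12-month anchor for renewal women is inferred from 2.3 and the annual cycle. The synopsis counts the year from fitting only. Section 2.5.5 adds the renewal date as an origin, but states it for the interim surveys.

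**Step 3: average duration behind the pooled mean.** Let r be the renewal share among raters. The protocol sets no quota, so r may lie anywhere from 0 to 100%. The values 20% and 40% are illustrative.

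Mean duration ≥ 12(1 − r) + 24r = 12 + 12r months.

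| r | Minimum mean duration (months) |
|---|---|
| 0 | 12 |
| 20% | 12 + 2.4 = 14.4 |
| 40% | 12 + 4.8 = 16.8 |
| 100% | 24 |

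At r = 100% nothing is mixed, but every rating then falls at about 24 months of use or more.

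**Step 4: effect on the PGI-I mean.**

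Pooled mean − new-user mean = r × (renewal mean − new-user mean).

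For a 1-point difference on the 7-point scale this is 0.2 at r = 20% and 0.4 at r = 40%. It is zero if the group means are equal.

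**Step 5: effect of the reference point alone.** As an assumed illustration, suppose new users score 2. Suppose renewal women would score 2 against their pre-Eclipse state but 4 against the time of joining, because they have been stable since. Under the pre-Eclipse reference the pooled mean is 2.0 at any r. Under the joining reference it is 2(1 − r) + 4r = 2 + 2r, which gives 2.2 at r = 10%, 2.5 at r = 25% and 3.0 at r = 50%. The women's condition is the same in both cases; only the comparison point has changed.

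**The case against.** The case on the other side has real substance.

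- **The reference point may already be right.** The second alternative in 2.5.3 is redundant for new users, so it may have been written to give renewal women the pre-Eclipse reference. The survey item is not shown and may be clear. This stands as a limit: the harm is possible, not demonstrated. The protocol text still does not assign the reference, so the point needs checking.
- **Renewal women may not be pooled at all.** On the contrary reading of 3.2 they are excluded. That is fair, but two defensible answers to who enters a named outcome is itself something to settle.
- **Pooling suits a registry.** This is a descriptive, open-label registry that enrolls renewal users on purpose. It has no comparator or stated hypothesis test, and a mean over all users is a legitimate description of it. That is correct as far as it goes. The pooled figure is not invalid, but it is hard to interpret as improvement after starting Eclipse.
- **The Vaizey difference is explained.** A change score cannot include women without a baseline. This is also correct. The two results would not contradict each other, but they would cover different enrolment groups in one report.
- **A split table belongs in an analysis plan.** An analysis plan could add one. However, 3.2 already prescribes the unsplit mean, and the reference point has to be right when the rating is given.
- **Selection may be weaker than it looks.** New users rated at an in-office 12-month visit may also be mostly continuers. This stands, and it limits the weight of the continuation argument.

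**Conclusion.** The concern holds and should be fixed. On the more natural reading of 3.1 and 3.2, the 12-month PGI-I mean pools women at about 12 months of use with women at about 24 months or more, and 2.5.3 does not fix one reference point for both.

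Neither the size nor the direction of any distortion can be determined from the protocol, and it may be zero. What the text supports is the difference in duration and a shift of r points in the pooled mean per 1-point difference between groups, with r unknown.

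The conclusion rests on three assumptions: that renewal women are included, that a renewal enrollee has about a year or more of prior use, and that her 12-month rating comes about a year after she enrolls. Confidence is medium, because the contrary reading of 3.2 is available and the survey wording cannot be seen.

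**What to change.** - **Section 2.5.3:** state one reference point for every subject, namely before she first started Eclipse. Check that the survey item says the same, and reword it only if it does not.
- **Section 3.2:** state that the PGI-I is reported separately, with n, for newly fitted and renewal subjects. The newly fitted group should be the same enrolment group as for the Vaizey change score. Any pooled mean is shown beside the split.

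The cost is one clarified phrase, one check of the survey item, one added sentence and one split table. The registry already knows how each woman entered. There are two downsides. Each group has a smaller n, and renewal women must recall further back (about 24 months or more at the 12-month rating, against about 12 for new users).

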## 1.3 LIBERATE

The LIBERATE study was a multi-center, prospective, open label clinical trial conducted at 11 centers in the United States. As with the prior studies, all IRBs approved the trial as an NSR investigation. The objective of this study was to evaluate the safety and effectiveness among treatment responders between 3 and 12 months.

Seventy-three (73) subjects met all study eligibility criteria and entered the 12-month Treatment Period to make up the Intent to Treat Cohort. The primary effectiveness endpoint was met: At 3 months, 73% (95% CI 61-82%,  $p < 0.0001$ ) of subjects met the success criterion, defined as a 50% or more reduction in the number of FI episodes. At 12 months, 70% (95% CI 58-80%,  $p < 0.0001$ ) met the success criterion. Additionally, throughout the study there were no serious device-related adverse events reported.

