### **2.2 Target Population**

Up to 150 subjects may be enrolled. All women being approached for inclusion into the PURSUIT registry must be adult female patients at participating sites and must have a diagnosis of Fecal Incontinence. She must be a new user of Eclipse or a patient returning to the clinic for her annual f/u visit. All participants will be required to provide informed consent and HIPAA authorization.

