### **2.5.5 Optional 3, 6 and 9 Month Surveys**

For the completion of online surveys at interim timepoints, a single survey generated using Survey Monkey containing the Eclipse Experience Assessment and the Vaizey score will be sent to subjects via a secure e-mail link or letter for completion approximately every 3 months after registering for the study. The electronic surveys are designed in such a way that there is no way to link a specific computer's IP address to the survey responses. For patients unable or unwilling to use the online survey, paper copies can be mailed to their addresses, with a pre-paid return envelope.

Subjects will have a 4 week window during which they can complete the surveys (every 3 months +/- 2 weeks) from their Eclipse Fitting date (or renewal date). If the surveys for the associated time period are not completed within this 4 week window, they will be counted as missed data points. Subjects will receive at least one, and no more than 5, reminders (by email and/or mail) to complete the surveys throughout the 4 week window.

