#### **4.11 Study Termination**

The study may be discontinued at Pelvalon's discretion for the following reasons:

- Occurrence of unexpected adverse events or unanticipated adverse device effects
- New scientific information that shows that the study is no longer valid or necessary
- Insufficient recruitment of subjects
- Persistent subject non-compliance with survey completion
- Business reasons

If the study is discontinued or suspended prematurely, Pelvalon will notify all participating subjects and the IRB promptly.

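### The 12-month PGI-I mean counts only completed assessments, so it is too favourable if fitted women who give no rating are less improved

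*Protocol*

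**What the plan says.** Protocol section 3.2 (Outcomes Measurements) names 12 months as the main time point: "Outcomes Measurements will be assessed at 12 months". Analyses at 3, 6 and 9 months are possible extras. The PGI-I runs from 1 (best) to 7 (worst) and has no baseline measurement. Its summary at a given time point is fixed: "the average PGI-I score will be computed as the mean score across all completed assessments".

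Section 3.1 (Analysis Population) defines the population: "The Analysis Data Set (ADS) will include all subjects who consent to participate in the PURSUIT registry and have at least an initial fitting". A woman already using the device enters through an administered renewal.

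Three other places bear on who supplies a rating:

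- Section 1.5.3 describes a short trial of one or more sizes before a woman qualifies for the year-long Insert, so some fitted women may go no further.
- Section 2.5.3 places the 12-month assessment at an in-office visit.
- Section 2.5.5 says of interim surveys not completed in their window that "they will be counted as missed data points".

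The protocol gives no rule for women without a rating in the PGI-I mean. It does not ask for the number answering to be shown against the Analysis Data Set, and it plans no sensitivity analysis.

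**The concern.** The data set and the estimator have different denominators. A woman who is fitted, finds that the device does not suit her and never moves past the Trial Insert belongs to the Analysis Data Set. She has little reason to attend a visit a year later and rate her improvement. The same holds for a woman who receives the Insert and then stops using it, since section 2.5.2 describes the annual contact as a renewal. Under section 3.2 such women drop out of the 12-month mean, and nothing in the reported figure shows that they did.

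The PGI-I is named among the outcome measures in the synopsis. Section 4.7 allows the results to be used in publications, marketing and regulatory submissions, and section 5.1 gives longer-term performance as what the registry is meant to show. A mean that describes only women who were still answering at 12 months could be read as describing everyone who was fitted.

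**Working it through.** **Stated figure.** There is none to reproduce. The protocol gives no expected PGI-I value, standard deviation, response rate or dropout rate. On numbers it says only "Up to 150 subjects may be enrolled".

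**Inputs from the protocol.** The scale is 1 to 7 with lower better, and the estimator is the mean of completed ratings (section 3.2). The target population is the Analysis Data Set (section 3.1).

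**Inputs that are assumptions.** The response share r, the responder mean mR and the non-responder mean mN.

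**Formula.**

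- All-women mean = r x mR + (1 - r) x mN
- Completed-only mean = mR
- Amount by which the completed-only mean is too favourable = (1 - r) x (mN - mR)

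The amount is positive if non-responders are less improved (mN above mR), zero if the means are equal, and negative if non-responders are more improved.

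**One case in full.** With mR = 2, r = 0.8 and mN = 4: 0.8 x 2 + 0.2 x 4 = 1.6 + 0.8 = 2.4. The protocol's rule reports 2.0, so the shift is 0.2 x 2 = 0.4. With mR = 2.5 instead, the all-women mean is 0.8 x 2.5 + 0.2 x 4 = 2.8, a shift of 0.3.

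**Range with mR = 2.** The completed-only rule reports 2.0 in every cell. The columns for mN = 1 and mN = 7 are the logical limits, which need no assumption about non-responders.

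| Response | mN = 1 | mN = 2 | mN = 3 | mN = 4 | mN = 5 | mN = 7 |
|---|---|---|---|---|---|---|
| 90% | 1.9 | 2.0 | 2.1 | 2.2 | 2.3 | 2.5 |
| 80% | 1.8 | 2.0 | 2.2 | 2.4 | 2.6 | 3.0 |
| 70% | 1.7 | 2.0 | 2.3 | 2.6 | 2.9 | 3.5 |
| 60% | 1.6 | 2.0 | 2.4 | 2.8 | 3.2 | 4.0 |
| 50% | 1.5 | 2.0 | 2.5 | 3.0 | 3.5 | 4.5 |

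**The same point through unequal response.** Suppose that 70% of women would score 2 and 30% would score 5. The true mean is 0.7 x 2 + 0.3 x 5 = 2.9.

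- Both groups answer at 80%: the reported mean is 2.9, with no shift.
- 80% against 60%: (0.56 x 2 + 0.18 x 5) / 0.74 = 2.02 / 0.74 = 2.73, too favourable by 0.17.
- 80% against 40%: (0.56 x 2 + 0.12 x 5) / 0.68 = 1.72 / 0.68 = 2.53, too favourable by 0.37. With 150 enrolled, 102 would answer.

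Missing ratings do no harm in themselves. The shift arises only when response is related to outcome.

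**The case against.** The strongest case against is that this is a single-arm, descriptive registry with no hypothesis or threshold for the PGI-I, so no decision rule is distorted. A mean at one time point can use only ratings that exist. Counts, imputation and bounds are usually left to a statistical analysis plan, which is not at hand, and section 3.2 does not forbid them. The protocol also works to limit non-response, through reminders for the interim surveys (section 2.5.5), queries about missing data (section 4.4) and compensation (section 4.10).

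Part of this stands. The completed-only mean is a legitimate summary, and the efforts to obtain data may keep the shift small. They do not change the estimator, however. Section 3.2 itself fixes the denominator, and it is the only PGI-I summary specified.

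A reader might infer more than the documents support:

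- **That non-return will be common.** The sponsor foresees the possibility, since "Persistent subject non-compliance with survey completion" is a listed reason for ending the study, but no rate is given. The optional surveys are those at 3, 6 and 9 months; the 12-month assessment belongs to an office visit.
- **That the figure will not be comparable with the 12-month result of LIBERATE (section 1.3).** That result is the proportion of women with at least a 50% reduction in episodes, which is a different endpoint, and the protocol plans no comparison. The quoted 70% (58-80%) does not settle its denominator either: 51/73 and 49/70 both round to it.
- **That ignoring earlier ratings is an error.** Using only the ratings of a time point for that time point's mean is coherent. Carrying forward a rating from a fitting visit could itself be too favourable for a woman who later stopped.

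**Conclusion.** The point holds as a conditional one. The rule in section 3.2 gives a 12-month PGI-I mean that is too favourable for the Analysis Data Set if the women without a rating are less improved than those with one. The direction follows from the scale. The size cannot be derived from the documents: it rests on an assumed response share and assumed means for both groups, and could be zero. Nothing in the protocol shows that response does depend on outcome. Failed fittings, stopped use and the tie to an office visit make such a link plausible, and that is the most that can be said.

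As planned, a reader of the result could not judge how far it might be off, because the number answering need not appear beside it. The change is worth making, but the registry does not stand or fall by it.

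**What to change.** In section 3.2:

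1. Keep the mean of completed ratings and label it as such.
2. At each time point, show the number answering out of all women in the Analysis Data Set whose time point has passed, including those whose fitting failed or who stopped the device. State from which date the months are counted for a woman who never received the Eclipse Insert, so that she cannot drop out of the count for want of a date.
3. Add a 12-month sensitivity analysis over that full denominator, with women who have no 12-month rating set to 4 and, as the worst-case bound, to 7. State that 4 is taken to mean no change. This is an assumption, because the protocol labels only the two ends of the scale, and the result is a scenario, not a bound.

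Do not carry earlier ratings forward to 12 months.

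The cost is a few lines of text and one extra table. It needs no new data and no change to visits. The downside for the sponsor is that a less favourable figure will stand beside the headline mean.

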## **4 Other Study Details**

---

### **4.1 Device Related Injuries and Product Complaints**

All device-related adverse events that result in serious injury will be summarized and tabulated based on the Medical Device Reporting (MDR) database maintained by Pelvalon, as required per 21 CFR 803. Product complaints will be summarized and tabulated based on the product complaint records maintained by Pelvalon, as required per 21 CFR 820.198.

### **4.2 IRB Approval**

Consistent with 21 CFR 56, and CFR 45 Part 160, and Subparts A and E of Part 164 (the Privacy Rule), this post market clinical study must be approved by an IRB prior to any subjects being enrolled.

### **4.3 Informed Consent**

The Sponsor will use an electronic Informed Consent Form and HIPAA Authorization form which is consistent with regulatory requirements in 21 CFR 50 and 45 CFR 46, and will be approved by the governing IRB prior to use. If sites or patients are unable to or unwilling to use the electronic forms, paper copies will be made available.

### **4.4 Monitoring**

The study will not be monitored but data will be reviewed on an ongoing basis and sites and/or subjects may be contacted by phone, email, or in writing to provide clarification of discrepant or missing data.

### **4.5 Recordkeeping and Record Retention**

Pelvalon will maintain evidence via an electronic / digital audit trail that electronic informed consent and HIPAA authorization was obtained prior to PHI being collected.

Pelvalon shall maintain study records for a minimum period of 2 years after the investigation is terminated or completed, or until the records are no longer required for purposes of supporting an FDA or International marketing approval, or such longer period as required by applicable law.

